Test		Cycle 1		Cycle 2		Cycle 3 subsequent o	6  and all cycles)	End of Treatment	28 day follow up after progression	Long- term follow- up r
Measure	Day -28 to treatment	Day 1	Day 15	Day 1	Day 15	Day 1	Day 15	Day of discontinuati on or within 7 days after		Every 3 months after 28- day follow up
Verification of available specimen for TGFβ 1,2,3 analysis p	Х	х		х	х	Xs			Х	
Blood biomarkers (including circulating cytokines) 1,p	х	х		х	х	х			Х	
Collection of buccal and fecal swabs for microbiome testing p	х			х		Xs		Х		
Verification of available specimen for PD-L1 expression m	х			х						
Collection of specimens for analysis of pharmacokinetics of M7824 n,p		х	X	Х				X		

aEnrollment will be done after the confirmation of fulfilling all screening inclusion criteria without matching any exclusion criterion. bPhysical examination should include a dermatological examination. If abnormal skin findings are observed, patient should be

referred to a dermatologist for biopsy of suspicious lesions. An ophthalmology examination including slit lamp evaluation inclusive of the anterior segment and with visual acuity should be conducted at Screening. At subsequent visits, eye signs and symptoms should be checked. If there are any clinically relevant findings then an appropriate ophthalmology examination including slit lamp evaluation inclusive of the anterior segment and with visual acuity should be obtained within 2 days. Starting with C1D15, a focused examination may be performed centered around patient's symptoms at an assigned visit.

°12-lead EKG should be performed as soon after completion of infusion as possible.

dEKGs are to be performed every 6 weeks.

eLaboratory draws may be performed up to 72 hours before a scheduled treatment.

fFor women of child-bearing potential. FSH should be drawn if clarification of post-menopausal state is warranted. Refer to Appendix 2 for further details.

gMandatory fresh tumor biopsies will be collected prior to treatment and prior to dose 3. An optional tumor biopsy following progression may be offered to the patient.

hPerformed on archival tissue or fresh biopsy. MSI testing performed in a CLIA certified laboratory is acceptable and does not need to be repeated (see section 6.4.5)

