aEnrollment will be done after the confirmation of fulfilling all screening inclusion criteria without matching any exclusion criterion. bPhysical examination should include a dermatological examination. If abnormal skin findings are observed, patient should be referred to a dermatologist for biopsy of suspicious lesions. An ophthalmology examination including slit lamp evaluation inclusive of the anterior segment and with visual acuity should be conducted at Screening. At subsequent visits, eye signs and symptoms should be checked. If there are any clinically relevant findings then an appropriate ophthalmology examination including slit lamp evaluation inclusive of the anterior segment and with visual acuity should be obtained within 2 weeks, unless an urgent necessity is determined by the treating provider that requires a sooner evaluation. Starting with C1D15, a focused examination may be performed centered around patient's symptoms at an assigned visit.

°12-lead EKG should be performed as soon after completion of infusion as possible.

dEKGs are to be performed every 6 weeks.

eLaboratory draws may be performed up to 72 hours before a scheduled treatment.

fFor women of child-bearing potential. FSH should be drawn if clarification of post-menopausal state is warranted. Refer to Appendix 2 for further details.

gMandatory fresh tumor biopsies will be collected prior to treatment and prior to dose 2 (i.e., on cycle 1, day 15) and prior to dose 3. An optional tumor biopsy following progression may be offered to the patient.

hMSI testing performed in a CLIA certified laboratory is acceptable and does not need to be repeated (see section 6.4.5)

iCMS on FFPE at CLIA testing laboratory on archival primary tissue or fresh biopsy.

jTumor measurements should occur with CT imaging or MRI. Ideally the same methodology would be used over the course of the study for a given patient. Bone scan should be done at screening if clinically indicated. For collection of those prior imaging studies prior to informed consent, readily available imaging studies since the onset of metastatic/unresectable disease are to be prioritized for collection. If the results of a CT scan or MRI performed within 4 weeks prior to first treatment are available, the screening CT and/or MRI does not need to be performed.

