The consensus molecular subtypes (CMS) are the best representation of the variation seen within CRC on the basis of gene expression. Briefly, CMS1 is characterized by hypermutated tumors with immune infiltrates and often associated with MSI-H. Notably, MSI-H is a subset of CMS1 and there is a proportion within this group that current biomarkers do not capture. CMS4 is a mesenchymal phenotype and is associated with a number of features associated with poor prognosis. Hallmark features of CMS4 include TGF $\beta$  activation, immune infiltration, EMT, matrix remodeling, and angiogenesis. In contrast to CMS1, the immune infiltration displays a relative absence of cytotoxic T cells but a high proportion of tumor associated macrophages (TAMs). TGF $\beta$  signaling and immune suppression in the microenvironment are contributory factors to the aggressive biology that is reflected in the poor overall survival within this group. TGF $\beta$  activation conditions stroma at other sites to form metastatic niches that promote a receptive environment for circulating tumor cells or increases tumor initiating cell capacity in conjunction with fibroblast activation. TGF $\beta$  inhibition with LY215299 in the TME prevented metastasis formation in patient derived tumor organoids. Blocking TGF $\beta$  signaling may help reverse a number of key processes in the CMS4 poor prognosis group which include: reversing fibroblast activation,

removing tumor initiating capacity, reversing immature myeloid and MDSC infiltration and downregulating EMT. Given the role of inflammatory cells and TGF $\beta$ , M7824 may reprogram an inflammatory response that is immune suppressive to an immunogenic response.

In a recent pilot study of patients with mCRC treated with M7824 monotherapy, there were 22 patients with adequate tumor tissue available for CMS subtyping. Patients here had been permitted to enroll without prior knowledge of CMS status. In this cohort, there were 10 patients with CMS4 mCRC. Only one of these ten patients demonstrated a radiographic response, which remained > 6 months in duration. Conclusions from this CMS4 cohort however were limited by the lack of available fresh paired tissue biopsies in order to understand better the intratumoral pharmacodynamics activity of M7824.

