- Physical examination will be performed prior to trial treatment on Day 1 (Cycle 1) and then prior to trial treatment according to **Tables 1-3**
- Eye signs and symptoms should be checked. If clinically relevant findings then an appropriate ophthalmology examination including slit lamp evaluation inclusive of the anterior segment and with visual acuity should be obtained within 2 days
- Dermatological assessments (assessments for skin lesions or rash with biopsy of suspicious lesions according to **Tables 1-3**)
- Vital signs, including body weight, will be assessed prior to trial treatment according to **Tables 1-3**.
- The 12-lead EKG will be assessed according to **Tables 1-3**.
- The laboratory hematology tests will be assessed prior to trial treatment according to **Tables 1-3**. Complete blood count results must be drawn and reviewed within 72 hours prior to dose administration.
- Full serum chemistry will be assessed prior to trial treatment according to **Tables 1-3**. Samples for full chemistry results must be drawn and reviewed within 72 hours prior to dose administration.
- A basic urinalysis will be performed prior to trial treatment every according to Tables 1-3.
- Samples for ANAs and RF according to **Tables 1-3**.

- A serum HCG pregnancy test will be required at Screening, urine or serum β-HCG pregnancy test will be performed prior to each administration of the study drug (if applicable).
- The tumor evaluation (see Section 6.3) will be performed prior to treatment at week 8, and then once every 8 weeks, with a tumor assessment visiting time window of 5 days prior to dosing. For subjects continuing treatment beyond 12 months (in consultation with the principal investigator), tumor evaluations should take place every 12 weeks.
- Tumor biopsies at Week 4, prior to the third treatment dose (-7 day window permitted). Archival tissue may be used in place of a fresh pretreatment biopsy if adequate tumor is available for analysis. If insufficient tissue is available for analysis for pretreatment tumor, then a mandatory fresh biopsy must be obtained. In cohort A, the site of tumor tissue for the pretreatment sample, whether archival or fresh, may be from the primary tumor or the metastasis. In cohort B, the site of tumor for the pretreatment sample, in order to classify the CMS subtype, must come from the primary tumor. The week 4, on-treatment biopsy for both cohorts may come from the primary tumor or from a metastatic site.

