iii. In peripheral blood, evaluation by circulating immune populations will include, but not be limited to,  $CD4^+$ ,  $CD8^+$ , NK,  $T_{reg}$ , monocytes and neutrophils as outlined by the Schedules of Assessments (**Tables 1-3**). High order flow cytometry panels will be designed. The panels will focus on 1) delineation of major immune cell types (T cells, B cells, NK cells, DC), 2) determination of T cell differentiation status and limited functionality (IFN $\gamma$ , TNF $\alpha$ , GB) and 3) defining the expression level of costimulatory and coinhibitory molecules on T cells. The proposed studies will be conducted retrospectively on cryopreserved PBMCs.

iv. Serum Cytokine Analyses. Cytokines (IFN- $\gamma$ , IL-1 $\alpha$ , IL-2, IL-4, IL-5, IL-8, IL-10, IL-12p70, IL-13, and TNF- $\alpha$ ) will be measured in the serum using the Meso Scale Discovery Platform (Rockville, MD). This technology allows for the detection of up to 40 analytes per well and uses a very low sample volume. This method has a sensitivity up to 1000 fold higher than traditional ELISA assays with a large linear range of 3-4 logs. The instrument performs immunoassays utilizing electrochemiluminescense to detect the signal in a 96 well plate format. This technology can be utilized for either single agent detection or in multiplex format. A wide menu of validated single or multiplex kits for the detection of 1 to 40 analytes are available from the manufacturer and can be customized.

d. Mutational profiling

- i. KRAS, NRAS and BRAF will be assessed via next generation sequencing in a panel of 409 genes that sequences known hotspots to a coverage of at least x250 coverage depth performed in the Molecular Diagnostic Laboratory (MDL) at MD Anderson. The lab is CAP accredited and CLIA certified to perform high complexity molecular testing for clinical purposes.
- ii. Tumor DNA analysis for KRAS, NRAS and BRAF performed in another CLIA certified molecular diagnostics laboratory do not need to be tested again
- iii. TGF $\beta$  signaling pathway mutations will also be assessed via this panel which will include, but not limited to, TGF $\beta$ R2, ACVR2A, SMAD2 and SMAD4.
- iv. RNA-seq and WES. This analysis will be performed using fresh frozen tissue specimens from CNB at MD Anderson Sequencing Facilities.

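### Sections 6.1.1, 6.1.2 and 6.4.5.3 allow an archival baseline and section 6.1.2 an unmatched week-4 site, against footnote g of Tables 1 and 2, and the paired biomarker tests do not restrict which pairs they use

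*Combined protocol and SAP*

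**What the plan says.** **Schedules.** Table 1 footnote g (Cohort A-C): "Mandatory fresh tumor biopsies will be collected prior to treatment and prior to dose 3". Table 2 footnote g (Cohort B): "Mandatory fresh tumor biopsies will be collected prior to treatment and prior to dose 2", and it goes on to require a further biopsy before dose 3.

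**Text.** Section 6.1.2: "Archival tissue may be used in place of a fresh pretreatment biopsy if adequate tumor is available for analysis". It then adds: "If insufficient tissue is available for analysis for pretreatment tumor, then a mandatory fresh biopsy must be obtained". For cohort A the baseline sample, "whether archival or fresh, may be from the primary tumor or the metastasis". For cohort B it has to be primary tumor, and the reason given is CMS classification. The week-4, "on-treatment biopsy for both cohorts may come from the primary tumor or from a metastatic site". Section 6.1.1 lists biopsies or an archived surgical specimen at screening. Section 6.4.5.3 has baseline markers run on archived tissue, with fresh tissue only preferred.

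**Assays.** For RNA-seq and WES, section 6.4.5 states: "This analysis will be performed using fresh frozen tissue specimens from CNB". Table 1 footnote m and Table 2 footnote n specify PD-L1 immunohistochemistry on fresh biopsy.

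**Analysis.** Exploratory objective 1 (section 3.3) and the first exploratory endpoint (section 7.3.3) rest on paired biopsies. Section 7.5.3.2 names a paired t-test or Wilcoxon signed rank test. None of these sections defines a pair.

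**The concern.** A paired test credits the mean within-patient difference to whatever separates the two samples. If the first is stored tissue from one site and the second a fresh biopsy from another, the difference contains site, tissue age and intervening therapy as well as M7824.

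In Cohort A-C every patient has progressed after checkpoint blockade (inclusion criterion 5a), and nothing stops the archival sample from predating it. The measured change could then include the effect of that earlier treatment. Cohort B patients have progressed on, or not tolerated, at least two prior lines (criterion 5b), and one metastasis is irradiated before dose 3. Nothing says whether the pre-dose-3 biopsy comes from the irradiated lesion, so direct radiation injury and out-of-field change can be pooled.

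The protocol itself treats fresh pairs as important. Section 2.2.5 says that conclusions from the earlier CMS4 patients were limited by the "lack of available fresh paired tissue biopsies".

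**Working it through.** The plan gives no sample size, effect size or SD for the paired-biopsy analysis, so there is no figure to reproduce. The check is mainly a comparison of the text.

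| Question | Footnote g, Tables 1 and 2 | Sections 6.1.1, 6.1.2, 6.4.5.3 |
|---|---|---|
| Is a fresh baseline required? | Yes, both cohorts | Under 6.1.2, only if archival tissue is insufficient; 6.1.1 and 6.4.5.3 admit archived tissue |
| Baseline site | Not stated | 6.1.2: primary or metastasis (A); primary (B, for CMS) |
| On-treatment site | Not stated | 6.1.2: primary or metastatic, both cohorts |
| Cohort B on-treatment timing | Before dose 2 (cycle 1 day 15) and before dose 3 | 6.1.1: before doses 2 and 4. 6.1.2: before dose 3. 6.4.5.3: before cycle 1 day 11 and before cycle 2 day 1 |

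**Step 1. Is there a contradiction?** Yes. A site with adequate stored tissue can follow section 6.1.2 and still breach footnote g.

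**Step 2. Does the analysis repair it?** No. No section requires the same lesion or organ, limits the age of archival tissue, requires sampling after the last prior therapy, or restricts the tests to fresh or site-matched pairs.

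**Step 3. Which markers are exposed?** Where fresh tissue is specified (PD-L1, RNA-seq/WES), an archival baseline means a missing pair, not a biased one. The archival problem therefore falls on immunohistochemistry and multiplex infiltrates and on FFPE-based expression. The site problem applies to any pair.

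**Step 4. How many pairs?** At most 15 in Cohort A-C. In Cohort B, at most 15 if it stops after stage one, otherwise 29. The archival or unmatched share is not given.

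**Step 5. Scale, under assumption only.** Suppose no drug effect, and a shift from site, age or prior therapy of d SDs of the paired difference. A two-sided 5% paired t-test then rejects with probability P(|T| > t(0.975, n−1)), where T is noncentral t with n−1 degrees of freedom and noncentrality d√n. For example, at n = 15 and d = 0.5, d√n = 0.5 × 3.873 = 1.94. The rows for half the pairs come from simulation (40,000 replicates, each pair shifted with probability one half).

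| Pairs shifted | d | n = 15 | n = 29 |
|---|---|---|---|
| None | 0 | 5% | 5% |
| All | 0.2 | 11% | 18% |
| All | 0.5 | 44% | 74% |
| All | 1.0 | 95% | 99.9% |
| Half | 0.5 | 14% | 25% |
| Half | 1.0 | 36% | 64% |

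The values of d and the shares are assumptions. The table shows only that a systematic shift would not average out at these sample sizes; it does not estimate the error in this trial.

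**The case against.** The strongest reply is that the documents can be read coherently. Table 2 lists confirmation of CMS status (footnote i: archival primary tissue or fresh biopsy) separately from tumor collection (footnote g: fresh). Inclusion criterion 6 and section 4.3.3 both tie stored primary tissue to CMS testing. On that reading archival primary tissue serves classification and fresh biopsies serve pharmacodynamics. The reply is reasonable for Cohort B, but the archival sentence in section 6.1.2 is not limited to CMS, so the text still needs to say so.

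A reader might go further and infer that every Cohort B pair could be an old primary against a fresh metastasis, since stored primary tissue is an entry requirement. The documents do not support leaning on that requirement, because its stated purpose is CMS assessment.

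A reader might also infer that Cohort B cannot separate drug from radiation. That is not so. The biopsy on cycle 1 day 15 precedes dose 2, and radiotherapy follows dose 2, so that sample reflects M7824 alone. Objective 1 for Cohort B also concerns M7824 with SBRT, which makes radiation part of the target. What remains open is irradiated versus non-irradiated lesions before dose 3.

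Finally, section 6.4.5 calls all biomarker analyses exploratory and dependent on available material, and the endpoint applies only where pairs exist. That stands, and it limits the weight of the point.

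**Conclusion.** The contradiction is certain. So is the absence of any rule on which pairs enter the tests in section 7.5.3.2. The bias is permitted by the text but not shown to occur: it depends on how many baselines are archival or from another site, and on a shift whose size and direction the documents do not give.

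It concerns exploratory objective 1 and its endpoint only. ORR, ctDNA clearance, PFS, DFS, OS and safety do not use these pairs, and Cohort D has no scheduled on-treatment biopsy. One assumption is that cohort A in section 6.1.2 means the current Cohort A-C.

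A reader might conclude that the trial repeats the gap described in section 2.2.5. That goes too far: on-treatment biopsies are mandatory in both cohorts, and the schedules call for fresh baselines. The text only leaves room for part of the gap to return.

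**What to change.** 1. Reconcile sections 6.1.1, 6.1.2 and 6.4.5.3 with footnote g, stating that archival primary tissue serves MSI, CMS and mutation classification. Reconcile the Cohort B biopsy timings in Table 2 footnote g and sections 6.1.1 and 6.4.5.3.
2. For each sample record the lesion, the organ, the collection date relative to the last prior therapy, and whether the lesion was irradiated.
3. In section 7.5.3.2 make the main paired analysis the fresh pairs taken after the last prior therapy from the same lesion or organ. Report archival or unmatched pairs separately and descriptively.
4. In Cohort B analyse the change to the pre-dose-2 sample (M7824 alone) and to the pre-dose-3 sample (M7824 plus radiation) separately, and split the latter by irradiated and non-irradiated lesions.

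The cost is protocol wording, a few data fields and fewer pairs in the main analysis, from cohorts of at most 15 and 29. No biopsy beyond those in footnote g is required. If sites have been working to section 6.1.2, some patients will have no fresh baseline. The analysis rule can then be applied to the fresh pairs that exist, without asking for further procedures.

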### 6.1.3 End of Treatment

### 6.1.3.1 End of Treatment Visit

All subjects must undergo an End-of-Treatment visit after discontinuation of M7824 for any reason. This visit should be performed on the day of or within 7 days after the decision to discontinue trial treatment but before any new antineoplastic therapy is started (if possible), whichever occurs earlier (see **Tables 1-3**). If it is known to the Investigator at the time of the End of-Treatment visit that the subject will start new treatment within 28 days of last treatment or they will be unable to return within 28 days of last treatment, assessments associated with the 28-Day Safety Follow-up visit may be conducted at the End-of-Treatment visit. For all these subjects, the discontinuation visit consists of:

- Documentation of AEs and concomitant medication.
- Physical examination including vital signs and body weight.
- Eye signs and symptoms should be checked. If clinically relevant findings then an appropriate ophthalmology examination including slit lamp evaluation inclusive of the anterior segment and with visual acuity should be obtained within 2 days.

- Dermatological assessments (assessments for skin lesions or rash with biopsy of suspicious lesions).
- Laboratory hematology, full serum chemistry, and basic urinalysis.
- ECOG performance status will be assessed.

## 6.1.4 Post Treatment Follow Up

### 6.1.4.1 28-Day Safety Follow Up

A Safety Follow-up visit is scheduled 4 weeks  $(28 \pm 5 \text{ days})$  after the last administration of M7824 but before any new therapy is started, if possible, whichever occurs earlier. If it is known to the Investigator at the time of the End of-Treatment visit that the subject will start new treatment within 28 days of last treatment or they will be unable to return within 28 days of last treatment, assessments associated with the 28-Day Safety Follow-up visit may be conducted at the End-of-Treatment visit. The 28-Day Safety Follow-up visit will comprise a full assessment for safety, immunogenicity, and tumor response as appropriate, which will include the following (refer to **Tables 1-3**):

- AEs, concomitant medications.
- Vital signs and body weight.
- Physical examinations.
- Eye signs and symptoms should be checked by the treating investigator. If clinically relevant findings then an appropriate ophthalmology examination including slit lamp evaluation inclusive of the anterior segment and with visual acuity should be obtained within 2 days.
- Dermatological assessments (assessments for skin lesions or rash with biopsy of suspicious lesions) by the treating investigator.
- The 12-lead EKG.
- Complete blood count, full serum chemistry.
- Full urinalysis.
- ECOG performance status will be assessed.
- The β-HCG pregnancy test (in females of childbearing potential).
- The tumor evaluation (only to be performed, if no disease progression was documented previously).
- Free T4, and TSH.
- Samples for ANAs and RF.
- The exploratory blood biomarkers including circulating cytokines and leukocyte subpopulations will be performed as detailed in **Tables 1-3** as described in Section 6.4.5.2.
- Samples for TGFβ determination.
- Blood samples for gene expression evaluation for subjects with PD.
- An optional tumor biopsy following progression may be offered to the patient.

